## 6.1.4.1 Bailout to an Alternate Thrombus Removal Strategy

If, during treatment of the high-risk PE, the subject requires additional thrombus removal therapy other than the Primary Treatment initiated, the additional therapy should be documented. The Clinical Events Committee (CEC, **Section 6.3**), will determine if the additional therapy meets the definition of Bailout for the purposes of analyzing the Primary Endpoint of the study. Definitions for Bailout are provided in **Table 4** below:

Initial Treatment Strategy/Primary Treatment:	Bailout to an Alternate Thrombus Removal Strategy Definition  :
Thrombolysis (systemic or catheter directed)	A bailout would be defined as the need for mechanical circulatory support or a different thrombus removal strategy at any time after the initial thrombolytic strategy was initiated. Applies when thrombolytic therapy alone was the original treatment plan ( conceived beforehand ). Note: if catheter directed thrombolysis (CDT) was the original treatment plan and emergent/clinically driven systemic thrombolytic administration (≥ 10 mg tPA or 5 mg TNK) was required after CDT was initiated, this would be considered a bailout. (Note: If the length of tPA or TNK administration is simply extended and is not emergent or clinically driven, this would not necessarily qualify as a bailout).
Anticoagulation (includes anticoagulation + ECMO)	A bailout would be defined as the need for thrombolytic therapy, mechanical circulatory support (if this was not part of the planned primary treatment), or a different thrombus removal strategy (for example, mechanical thrombectomy, open embolectomy, etc.) at any time after the initial anticoagulation strategy was initiated. Anticoagulation alone was the original treatment plan ( conceived beforehand ).
Surgical Thrombectomy	A bailout would be defined as the need for a different thrombus removal strategy or the addition of mechanical circulatory support once a surgical approach was initiated. Surgical thrombectomy alone was the original treatment plan ( conceived beforehand ).
Mechanical Thrombectomy (Includes FlowTriever and non-FlowTriever thrombectomy)	A bailout would be defined as the need for a different thrombus removal strategy, the addition of mechanical circulatory support, or surgical thrombectomy once a percutaneous mechanical thrombectomy approach was initiated. Low-dose catheter directed adjunctive thrombolytic therapy (less than 10 mg tPA or 5 mg TNK) that is administered intra-procedurally or post-procedurally will be discouraged but not considered a bailout.
	
 
Note:
 
Completion of the FlowTriever procedure will be defined as the final removal of the FlowTriever catheter from the patient.
 
If mechanical circulatory support was placed before mechanical thrombectomy was initiated as part of the planned treatment strategy, this is not considered a bailout. If, however; mechanical
 

## Table 4: Bailout Definitions

Bailout measures will be reviewed and adjudicated by the Clinical Events Committee for the purposes of analyzing the Primary Endpoint.

## 6.1.4.2 Clinical Deterioration

Subject clinical status will be monitored and recorded in the study records. Signs of clinical deterioration observed from the time of initiation of the Primary Treatment for high-risk PE through hospital discharge will be recorded by the site and adjudicated by the Clinical Events Committee (CEC, **Section 6.3**), and is defined in **Table 5** below.

## Table 5: Clinical Deterioration Definition

Clinical	Deterioration  , defined as:
•	Need for CPR after primary treatment initiation, or
•	Need to start IV vasopressors to keep systolic blood pressure > 90 mmHg in a previously normotensive patient after primary treatment initiation, or
•	Need for mechanical ventilation after primary treatment initiation in a previously spontaneously breathing patient, or
•	Need for noninvasive positive pressure ventilation after primary treatment initiation in a patient previously on nasal cannula

Clinical Deterioration will be reviewed and adjudicated by the Clinical Events Committee for the purposes of analyzing the Primary Endpoint.

## 6.1.4.3 Major Bleeding

All bleeding events related to the patient's high-risk pulmonary embolism or its treatment should be recorded as adverse events by study sites. The CEC will review and adjudicate bleeding events for the purposes of analyzing the primary endpoint. Bleeding events which meet the BARC 3b/3c/5a/5b definition of Major Bleeding will be included in the Primary Endpoint analysis. The BARC 3b/3c/5a/5b Major Bleeding Definition is provided in Table 6 below:

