Major bleeding events occurring from the time of initiation of the Primary Treatment therapy through hospital discharge will be documented as adverse events and subsequently adjudicated by the CEC. See Section 6.1.4.3 for details. Only Adverse Events (AEs) related to the subject's PE condition and its treatment should be reported in the FLAME study.

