## 6.2 SAFETY DATA HANDLING AND REPORTING

## 6.2.1 Adverse Event Definition and Assessment

An Adverse Event (AE) is an untoward medical occurrence or exacerbation of an existing medical condition subsequent to enrollment in the study. AEs are assessed for severity, seriousness, and relationship to treatment devices and procedures, as defined in Table 7.

The study will only capture AEs related to the subject's PE condition and treatment. Reportable AEs include all events considered in the safety analyses, all thrombus removal therapy/device- and/or procedure-related AEs, as well as events resulting in death.

AE Assessment	Categories and Definitions
Severity:	Mild: No limitation of usual activities, no therapy or only symptomatic therapy required to treat the injury or illness

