## 6.2.2 Site Reporting of Adverse Events

The study was designed to capture real world data regarding the clinical use of the FlowTriever System and other high-risk PE treatments. The study follows guidelines for Instructions for Use and physician discretion for PE treatment.

This is a data collection study only; there is nothing investigational or experimental in the subject's medical treatment and the subject will be treated per standard of care. **Therefore, the study will only capture AEs related to the subject's PE condition and treatment.** Reportable AEs include all events considered in the safety analyses, all thrombus removal therapy/device- and/or procedure-related AEs, as well as events resulting in death. The AEs will be captured on the AE CRF and should include, wherever possible, severity, duration, outcome, the Investigator's description the event, and its relationship to the thrombus removal therapy/device, to the thrombus removal procedure or any subsequent procedures, or to a thrombolytic agent or anticoagulant.

- Non-serious reportable AEs are to be submitted via the electronic data capture system (EDC) in a timely fashion.
- Reportable SAEs must be reported to the Sponsor within 5 business days of the Investigator's knowledge of the event. The event is reported in the EDC.

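### The protocol gives sites conflicting rules for recording major bleeding, so a non-fatal primary-endpoint bleed judged unrelated could go unreported

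*Protocol*

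**What the plan says.** **Endpoint.** Protocol Tables 1, 6 and 10 and SAP Table 1 define major bleeding by BARC grade alone. Section 6.1.4.3 confirms the counting rule: "Bleeding events which meet the BARC 3b/3c/5a/5b definition of Major Bleeding will be included in the Primary Endpoint analysis". The only mention of relatedness in the definition ties the hemoglobin drop to the bleed, not the bleed to the embolism or its treatment.

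**Text that limits recording.**
- Section 6.1.4.3: "All bleeding events related to the patient's high-risk pulmonary embolism or its treatment should be recorded as adverse events by study sites".
- Table 3 footnote 9, on the general adverse-event row: "Only Adverse Events (AEs) related to the subject's PE condition and its treatment should be reported in the FLAME study".
- Section 6.2.1: "The study will only capture AEs related to the subject's PE condition and treatment". Section 6.2.2 repeats this in bold, and the adverse-event entry in Table 10 repeats it again.

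**Text that does not limit recording.**
- The second of the two Table 3 footnotes numbered 8, on the major-bleeding row: "Major bleeding events occurring from the time of initiation of the Primary Treatment therapy through hospital discharge will be documented as adverse events". It then sends them to the CEC.
- Sections 6.2.1 and 6.2.2 and Table 10, directly after the limiting sentence: "Reportable AEs include all events considered in the safety analyses". Events resulting in death are also reportable.

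**Who sees what.** Under section 6.3 the CEC adjudicates site-reported data, and determining relatedness is one of its own tasks. Treatment is chosen by the physician, and data come from chart review (6.1.3.1, 6.1.3.2). No blinding of sites is described.

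**The concern.** A primary-endpoint component should be captured by a rule at least as wide as its definition. Here the section that governs bleeding has a narrower rule than the definition it serves, and other passages contradict it. Two coordinators could handle the same bleed differently and both be following the protocol. The CEC cannot adjudicate a bleed that never reaches it.

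The error runs in one direction. An omitted bleed either changes nothing, because the subject already has another component event, or removes an event from the FlowTriever count. Success is judged against a fixed 32% goal with no randomized comparator in which the same omission would cancel, so any loss favours success.

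Clinical deterioration is handled differently: section 6.1.4.2 has sites record it from treatment initiation to discharge with no relatedness condition. Bleeding is exposed because it is captured as an adverse event, where the limit applies.

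**Working it through.** **1. The rules applied to one case.** Take a non-fatal 3b or 3c bleed that the site attributes to something other than the embolism or its treatment.

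| Text | Recorded? |
|---|---|
| 6.1.4.3 | Not requested |
| Table 3 footnote 9; limiting sentence in 6.2.1, 6.2.2 and Table 10 | No |
| Table 3 footnote 8 (major bleeding) | Yes |
| Reportable-events sentence in 6.2.1, 6.2.2 and Table 10 | Yes, since each primary component is also a secondary safety endpoint (Table 2) |
| Endpoint definition | Counts if it reaches the CEC |

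A fatal bleed (5a/5b) is not at risk. It is an all-cause death, and deaths are reportable.

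**2. The plan's decision rule.** Inputs from Protocol 7.1 and Table 8: goal 0.32, N = 50 then 71, z = −2.0311 then −1.7116.
- Interim: 0.32 − 2.0311 × √(0.32 × 0.68 / 50) = 0.186, or 9.30 events. The cut is 9.
- Final: 0.32 − 1.7116 × √(0.32 × 0.68 / 71) = 0.2252, or 15.99 events. Sixteen events give z = −1.7097, which just misses, so the working cut is 15 although Table 8 prints 16.0.

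Both thresholds agree with Table 8. At the interim, 9/50 gives z = −2.12 (passes) and 10/50 gives z = −1.82 (does not).

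**3. Exact probability of declaring success.** With p the recorded event rate:

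P(success) = P(X₅₀ ≤ 9) + Σ over x = 10 to 15 of P(X₅₀ = x) × P(X₂₁ ≤ 15 − x)

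At p = 0.32 this is 3.9%.

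**4. Effect of lost bleeds.** Assume a true rate of 32% and a loss of

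L = (bleeding rate) × (share called unrelated and omitted) × (share of those that are the subject's only event)

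so that the recorded rate is 0.32 − L. The bleeding rate is the 11.5% pooled in Table 9. The other two shares are assumptions, with one half used for the last.

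| Called unrelated | L (points) | False success |
|---|---|---|
| 0% | 0 | 3.9% |
| 5% | 11.5 × 0.05 × 0.5 = 0.29 | 4.3% |
| 10% | 11.5 × 0.10 × 0.5 = 0.58 | 4.7% |
| 20% | 11.5 × 0.20 × 0.5 = 1.15 | 5.8% |

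**5. Range over the Table 9 interval for bleeding (6.0% to 21.0%), still with one half.**
- 10% called unrelated: L = 0.30 to 1.05 points; false success 4.3% to 5.6%.
- 20% called unrelated: L = 0.60 to 2.10 points; false success 4.8% to 7.9%.

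If the final cut were read as 16, the chance with nothing lost would already be 5.9%. It would be 6.5%, 7.2% and 8.7% for the three shares in step 4.

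**The case against.** The strongest reply is that the protocol, read as a whole, already requires full capture. Table 3 gives major bleeding its own row and footnote with no relatedness condition; the restrictive footnote belongs to the general adverse-event row. The limiting sentence in 6.2.1 and 6.2.2 is followed at once by one that makes every event in the safety analyses reportable. Section 6.1.4.3 asks for all related bleeds and does not say that others must be withheld. This stands: a reader might infer that sites are told to record only related bleeds, so that a filter is built into the design, and the documents do not support that.

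It also stands that few bleeds would be affected. The limit covers the embolism and its treatment, and 6.2.2 asks about relationship to anticoagulants and thrombolytics as well as device and procedure. A major in-hospital bleed outside all of these should be uncommon. The 11.5% is a literature rate for other therapies, and section 1.6.5 expects less thrombolytic bleeding with FlowTriever.

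Monitors check that data are complete (6.7), and source records can be inspected (6.10.2). That weakens any suggestion of an unchecked omission, but a monitor checks against the protocol, and the protocol does not say which rule prevails. That the site judges relatedness is itself an inference: 6.1.4.3 names no judge, but the site decides what it enters.

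**Conclusion.** The point holds as a conflict between capture rules for a primary-endpoint component. The exposure is confined to non-fatal 3b and 3c bleeds that a site regards as unrelated, and it affects the result only where the bleed is the subject's sole component event. Within that group the bias can only favour success.

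The size is probably small. On the assumptions in the working, false success stays below the nominal 5% when 5% or 10% of bleeds are called unrelated (4.3% and 4.7%) and passes it at 20% (5.8%). These figures illustrate sensitivity and do not estimate what will happen: neither the share called unrelated nor the one-half comes from the documents. A reader might also infer that type I error is already inflated; that does not follow either. The case for acting is that the ambiguity is real, one-directional and cheap to remove. Sample size, boundaries and analysis are unaffected.

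**What to change.** - **Section 6.1.4.3:** state that every bleed that may meet BARC 3b/3c/5a/5b, from initiation of the primary treatment through discharge or study exit, is recorded and sent to the CEC regardless of relatedness.
- **Table 3 footnote 9, sections 6.2.1 and 6.2.2, and the adverse-event entry in Table 10:** after the limiting sentence add an exception for potential primary-endpoint events, which are reported regardless of relatedness.
- **Case report form:** carry the same instruction.

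The requirement should stop at bleeds that may meet the endpoint definition. Asking for every minor bleed regardless of cause would add work without informing the primary analysis. The cost is protocol and form wording and a few more bleeding entries.

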## Table 6: Major Bleeding, BARC 3b/3c/5a/5b Definition

## Major Bleeding (BARC 3b/3c/5a/5b), defined as:

- 3b: Overt bleeding plus hemoglobin drop of ≥ 5 g/dL (provided hemoglobin drop is related to bleed); cardiac tamponade, bleeding requiring surgical intervention for control (excluding dental/nasal/skin/hemorrhoid); bleeding requiring intravenous vasoactive agents
- 3c: Intracranial hemorrhage (does not include microbleeds or hemorrhagic transformation, does include intraspinal), subcategories confirmed by autopsy or imaging or lumbar puncture, intraocular bleed compromising vision.

- 5a: Probable fatal bleeding; no autopsy or imaging confirmation but clinically suspicious
- 5b: Definite fatal bleeding; overt bleeding or autopsy or imaging confirmation

Major bleeding events will be reviewed and adjudicated by the Clinical Events Committee for the purposes of analyzing the Primary Endpoint.

## 6.1.5 Hospital Discharge

Subjects data will be collected through discharge from the hospital from their index-treatment for highrisk PE. Utility measures will be collected including, but not limited to:

- Length of hospital stay
- Length of ICU stay
- Use of ECMO, including either pre- or post-treatment initiation and duration
- Time to extubation, if intubated
- Discharge location

## 6.1.6 Study Exit

Subjects may be exited from the study if they are deceased prior to discharge. As this study is only looking at outcomes through hospital discharge, it is not expected that subjects will be lost to follow-up. Subjects who remain in-hospital (from the index hospitalization for high-risk PE) for  $\geq$  45 days after the Primary Treatment for high-risk PE will be exited from the study at that time, as the study is considering acute outcomes for the treatment of high-risk pulmonary embolism.

Study Exit for all subjects, regardless of reason, will be documented on a Study Exit form in the study record.

## 6.2 SAFETY DATA HANDLING AND REPORTING

## 6.2.1 Adverse Event Definition and Assessment

An Adverse Event (AE) is an untoward medical occurrence or exacerbation of an existing medical condition subsequent to enrollment in the study. AEs are assessed for severity, seriousness, and relationship to treatment devices and procedures, as defined in Table 7.

The study will only capture AEs related to the subject's PE condition and treatment. Reportable AEs include all events considered in the safety analyses, all thrombus removal therapy/device- and/or procedure-related AEs, as well as events resulting in death.

AE Assessment	Categories and Definitions
Severity:	Mild: No limitation of usual activities, no therapy or only symptomatic therapy required to treat the injury or illness

## **Table 7: Site Assessment of Adverse Events**

	Moderate: Some limitation of usual activities or specific therapy is required				
	Severe: Inability to carry out usual activities, hospitalization, emergency treatment, life threatening events, or death				
Seriousness:	
 
Serious Adverse Event (SAE): An AE which is at least one of the following: 
 
Is fatal
 
Is life-threatening
 
Results in persistent or significant disability/incapacity
 
Results in permanent impairment of a body function or permanent damage to a body structure
 
Results in hospitalization or prolongs a hospitalization
 
Necessitates medical or surgical intervention to preclude permanent impairment of a body function or permanent impairment of a body structure
 
 
 
				
Relatedness (assessed for any thrombus removal strategy or procedure):	Not Related: The clinical event is completely independent of thrombus removal therapy or procedure and/or evidence exists that the event is related to another etiology.				
	Related: The clinical event occurs in a plausible time relationship to the thrombus removal therapy or procedure and cannot be explained by any concurrent disease or other devices or procedures.				
	Unknown: The relationship to the thrombus removal therapy or procedure is not known.				

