## 5.1.2 Secondary Endpoints

Secondary endpoints include safety endpoints as well as utility measures which will be assessed in the FlowTriever Arm. Details of the secondary endpoints are provided in Table 2 below.

Subjects enrolled in the Context Arm will be analyzed separately from the endpoint analysis utilizing descriptive methods.

Secondary Endpoints	Secondary Safety Endpoints				
	
 
Frequency of each primary endpoint composite component
 
				
	
 
Frequency of stroke (ischemic or hemorrhagic)
 
				
	
 
Frequency of device-related complications
 
				
	
 
Access site injury requiring intervention, both venous and arterial
 
				
	Utility Measures				
	Length of hospital stay				
	Length of ICU stay				
	
 
Use of ECMO, including either pre- or post-treatment initiation and duration
 
				
	Time to extubation, if intubated				
	Discharge location				

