## 6.3 CLINICAL EVENTS COMMITTEE (CEC)

A Clinical Events Committed (CEC) will be utilized in this study for the purposes of adjudicating the primary and secondary endpoints. Site-reported safety and outcome data will be provided to the CEC for review and adjudication of the following items for all FlowTriever and Context Arm subjects enrolled in the study:

- Classification as a Serious Adverse Event (SAE)
- Determination of relatedness
- Assessment of severity
- Assessment of endpoint criteria

Adjudication will be conducted according to the FLAME CEC Charter.

(Note that the primary endpoint will only be analyzed for subjects in the FlowTriever Arm of the study, but the CEC will adjudicate events for subjects enrolled in the Context Arm of the study as well)

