## Table 10: Terms and Definitions

Term or Phrase	Definition			
Device-related complications	Complications related to devices used for thrombus removal. Complications related to Primary Treatment devices and bailout devices used will be adjudicated by the CEC. Note that complications related to ECMO should be included here where ECMO was part of the Primary Treatment strategy.			
Discharge Location	The location where the patient is discharged from the hospital, may include but not limited to home, home with home healthcare, skilled nursing facility, hospice, etc.			
FlowTriever Arm	FlowTriever Arm subjects are defined as those subjects where FlowTriever is used as the primary thrombus removal treatment for pulmonary embolism. FlowTriever Arm subjects will be the primary population utilized to evaluate the study Primary Endpoints for study success.			
Glasgow Coma	The Glasgow Coma Scale provides a practical method for assessment of impairment of			
Scale	conscious level in response to defined stimuli.			
High-risk Pulmonary Embolism (PE)	
 
Pulmonary embolism with the following signs/symptoms:         
 
Systolic blood pressure <90 mmHg for at least 15 minutes or drop of >40 mmHg in systolic blood pressure for at least 15 minutes, and/or
 
Need for vasopressor support, and/or
 
Resuscitation after cardiac arrest with <30 minutes of CPR and Glasgow Coma Scale >8.
 
 
 
			
Length of Hospital Stay	Time from admission to the hospital for pulmonary embolism treatment until discharge from the hospital post-treatment. For subjects who do not survive until hospital discharge, the length of hospital stay will be from the time of admission until the time of death.			
Length of ICU Stay	Time from admission to the ICU until time of discharge from the ICU. Multiple ICU stays within the same hospital admission (index hospitalization for high-risk PE) will be recorded.			

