Major Bleeding, BARC 3b/3c/5a/5b definition	
 
3b: Overt bleeding plus hemoglobin drop of ≥ 5 g/dL (provided hemoglobin drop is related to bleed); cardiac tamponade, bleeding requiring surgical intervention for control (excluding dental/nasal/skin/hemorrhoid); bleeding requiring intravenous vasoactive agents
 
3c: Intracranial hemorrhage (does not include microbleeds or hemorrhagic transformation, does include intraspinal), subcategories confirmed by autopsy or imaging or lumbar puncture, intraocular bleed compromising vision.
 
5a: Probable fatal bleeding; no autopsy or imaging confirmation but clinically suspicious
 
5b: Definite fatal bleeding; overt bleeding or autopsy or imaging confirmation
 
			
Primary Endpoint	
 
In-hospital composite endpoint of:
 
All-cause mortality
 
Bailout to an alternative thrombus removal strategy
 
Clinical deterioration
 
Major bleeding, BARC 3b/3c/5a/5b definition
 
			
Primary Treatment Strategy	The initial treatment strategy for thrombus removal (for the high-risk PE) determined by the treatment team prior to treatment initiation and documented.			
Prior Therapy Arm	Subjects presenting with low/intermediate-risk PE who receive advanced therapy during their hospital stay but subsequently progress to high-risk PE in the same hospital stay should be enrolled in the Prior Therapy Arm.			

Term or Phrase	Definition			
Protocol Deviation	A protocol deviation is a divergence or non-adherence from the protocol-specific study procedures. Protocol deviations should be recorded for all assessments not collected and issues related to eligibility criteria.			
Relatedness of Adverse Event	
 
Unrelated: The clinical event is completely independent of study procedure/study device/study treatment and/or evidence exists that the event is related to another etiology.
 
Related: The clinical event occurs in a plausible time relationship to study procedure/study device/treatment and cannot be explained by any concurrent disease or other devices, drugs or chemicals.
 
Unknown: The relationship to the study procedure/study device/treatment is not known.
 
			
Screen Failure	Patients who do not meet eligibility criteria for enrollment in the study. Screen failure patients will not be entered into the study database/EDC system, and will not be assigned a study subject ID.			

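### The Related definition demands that other causes be ruled out, differs between Protocol Tables 7 and 10, and is likely to under-count device-related complications

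*Protocol*

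**What the plan says.** Protocol 5.1.2 and SAP 2.3 list "Frequency of device-related complications" among the secondary safety endpoints. Protocol 7.4.2 and SAP 5.4 analyse it descriptively.

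Table 7 (Protocol 6.2.1) gives the site three classes:
- **Related:** plausible timing, and the event "cannot be explained by any concurrent disease or other devices or procedures".
- **Not Related:** the event is wholly independent of the therapy or procedure, and/or "evidence exists that the event is related to another etiology".
- **Unknown:** "The relationship to the thrombus removal therapy or procedure is not known".

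Table 10 (Protocol section 10), whose terms are said to apply across the study and its reporting, uses the same three classes. There, a Related event is one that "cannot be explained by any concurrent disease or other devices, drugs or chemicals".

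Protocol 6.3 gives the CEC the "Determination of relatedness" for FlowTriever and Context Arm subjects and adds: "Adjudication will be conducted according to the FLAME CEC Charter". The Table 10 entry for this endpoint says: "Complications related to Primary Treatment devices and bailout devices used will be adjudicated by the CEC". It does not redefine what related means.

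**The concern.** The test for Related works by exclusion: a competing explanation of a listed kind is enough to fail it, even if the device also contributed. In this population a competing explanation is built in. Protocol 5.4.1 requires that PE be judged the cause of shock. Protocol 5.4.2 excludes subjects with a contraindication to anticoagulants, so anticoagulation should be common, although a footnote to Table 3 says it is not required.

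Arrest, hypotension or hypoxia around the procedure will often be explainable by the embolism, and bleeding by the anticoagulant. Such events can leave the Related class without anyone judging that the device played no part.

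At stake is the reading of one of the few endpoints that speak directly to the device. Protocol 6.8 also names a possible device-related hazard among the grounds for stopping the study, and under-attribution would weaken that signal.

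**Working it through.** The documents give no rate, power or derivation rule for this endpoint, so there is no stated figure to reproduce. The check is a comparison of the texts, followed by an illustration of size.

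**1. The two definitions side by side**

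| Competing explanation | Table 7: blocks Related? | Table 10: blocks Related? |
|---|---|---|
| Concurrent disease | Yes | Yes |
| Other devices | Yes | Yes |
| Other procedures | Yes | Not listed |
| Drugs or chemicals | Not listed | Yes |

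**2. Three events run through both tables**
- *Arrest during thrombectomy in a subject already in shock from PE.* Concurrent disease can explain it, so it is not Related under either table. It goes to Unknown, or to Not Related if there is evidence that the embolism was the cause.
- *Access-site bleed on heparin, with no other device or procedure involved.* Table 7 does not list drugs, so the bleed can be Related. Table 10 does list them, so it is not Related. The same case can be classed two ways.
- *Vessel perforation or device breakage.* Neither PE nor a drug naturally explains it, so it can be Related under both.

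**3. Who decides, and by which text**
Table 7 is headed as the site's assessment, and the CEC decides relatedness for the two arms concerned. The standard it applies is in a Charter that is not among the documents. Of the definitions that are available, Table 10 is the one declared study-wide.

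**4. How Unknown is counted**
Neither Protocol 7.4.2 nor SAP 5.4 says. Because the endpoint is worded as complications related to devices, the natural reading leaves Unknown out, but that is an inference.

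**5. Size, by illustration**
Let q be the true share of subjects with a complication to which the device contributed, and s the share of those classed Related. Both are assumed. N = 71 is the maximum FlowTriever Arm size (Protocol 5.2.1).

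Expected counted events = 71 × q × s. Probability that none is counted = (1 − q × s)^71.

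| q | s | Expected events | P(none counted) |
|---|---|---|---|
| 5% | 1 | 71 × 0.05 = 3.55 | 0.95^71 = 2.6% |
| 5% | 0.5 | 71 × 0.025 = 1.78 | 0.975^71 = 16.6% |
| 5% | 0.25 | 71 × 0.0125 = 0.89 | 0.9875^71 = 40.9% |
| 10% | 1 | 71 × 0.10 = 7.10 | 0.90^71 = 0.1% |
| 10% | 0.5 | 71 × 0.05 = 3.55 | 2.6% |
| 10% | 0.25 | 71 × 0.025 = 1.78 | 16.6% |

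A confidence interval does not absorb this error. If 10 of 71 subjects had such an event and only 2 were classed Related (a pessimistic s of 0.2, also assumed), the report would show 2/71 = 2.8% (exact 95% CI 0.3 to 9.8) instead of 10/71 = 14.1% (7.0 to 24.4).

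**6. Reach**
No component of the primary composite requires the Related class, so its design (32% goal, 18% expected, looks at 50 and 71) is unaffected.

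**The case against.** A reader might infer that a Related classification is almost impossible in this population, so that the endpoint is driven to zero and the device looks safe whatever happens. The documents do not support that. Mechanical injuries and device failures can pass the test, and no figure shows how many events would fail it. In the illustration the count comes close to zero only if nearly every true device event fails.

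A reader might also take it as a rule that Unknown events are not counted. No text says so; their handling is simply unspecified.

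Other points on this side stand:
- The CEC, not the site, settles relatedness, and its Charter may use a better standard. That limits certainty but does not cure the problem. Nothing supplied shows a different standard, and Table 10 is meant to apply throughout.
- Drugs block a Related class only under Table 10, so the anticoagulant argument does not rest on Table 7's Related wording.
- Many of the serious outcomes are counted elsewhere without this test: death from any cause, CPR, new ventilation, bleeding that meets the BARC definition, stroke, and access-site injury requiring intervention.
- Protocol 6.2.2 already has sites record, where possible, the relationship to the device, the procedure and a thrombolytic or anticoagulant.
- The endpoint is descriptive, with no test attached.

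Together these limit the consequence. They do not reconcile the two tables, and they do not give an event with two causes a place in the device-related count.

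**Conclusion.** The point holds in a limited form. The Related definition is exclusionary, has no intermediate grade, sits beside a Not Related class that evidence of another cause can satisfy, and differs between Tables 7 and 10. Events caused jointly by the device and PE, or under Table 10 by the device and a drug, are likely to be lost from the device-related count. The direction is downward. The amount cannot be derived from the documents, and the figures above rest on assumed values of q and s.

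The conclusion also assumes that the CEC works from wording like that of Table 10, which the unseen Charter could contradict. The conflict between the tables needs no assumption. The effect is confined to a descriptive secondary endpoint and to hazard detection. This is a cheap improvement, not a threat to the primary result.

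**What to change.** 1. Put one identical definition in Table 7, Table 10 and the CEC Charter: an event is Related if there is a reasonable possibility that the device or procedure caused or contributed to it, with no requirement that other causes be excluded.
2. State in Protocol 6.3 that the CEC applies this definition.
3. In Protocol 7.4.2 and SAP 5.4, report the Related count, with Related-plus-Unknown beside it as a sensitivity count. It should not be the headline rate, because treating every Unknown as device-related would err in the other direction.

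The third step cannot replace the first: a Related-plus-Unknown count does not recover two-cause events already classed Not Related.

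The cost is wording in the protocol, Charter and SAP, with the same cases and the same committee, and a somewhat less favourable device-related rate.
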